|---------------------------|---------------------------|----------------------------|--|
| - up to 18 months: | every 9 weeks             | weeks after randomisation: | 9, 18, 27, 36, 45, 54, 63, 72, 81 (+/- 1 week) |
| - up to 2 years:   | every 12 weeks            | “                          | 93, 105 (+/- 1 week)                           |
| - years 3 and 4:   | every 6 months (26 weeks) | “                          | 131, 157, 183, 209 (+/- 1 week)                |
| - at 5 years:      |                           | “                          | 260 (+/- 1 week)                               |
- In case of clinical suspicion of distant metastases, immediate adequate diagnostic procedures including CT-scan, whole body PET-CT, bone scans and MRI (as appropriate) should be used.  
Early progression at 9 weeks: Patients with tumour volume increase documented by CT scan 9 weeks after randomisation, but without appearance of new lesions or rapid clinical deterioration should continue to be treated with IMP and clinically observed with a stringent imaging schedule 4 weeks later to determine whether there has been a decrease in the tumour size or disease stabilisation, or alternatively continued PD which would terminate the trial treatment.  
Patients who discontinue study treatment for reasons other than progressive disease: Restaging should be repeated at time of discontinuation, except if already performed within 6 weeks prior to the last dose of study treatment.
- 14 **Adverse events:** All adverse events that occur within 100 days of the last administered study medication or within 100 days after the last visit in the observation arm must be documented. Symptoms present at baseline and at randomisation will be recorded on the adverse event forms as well.
- 15 **Thoracic radiation** will be administered concurrently to chemotherapy and should preferentially start at the same time as the first chemotherapy cycle (e.g. day 1 of cycle 1), if the patient can be enrolled before chemotherapy start. Otherwise, radiotherapy should optimally start at day 1 of cycle 2, i.e. in treatment week 4. As a latest start of radiotherapy day 1 of cycle 3 is allowed, but should be exceptional.

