### **16.6. During consolidation phase (induction and maintenance)**

Within 3 days before the administration of the next dose, the following evaluations will be done.

In the observation arm, these evaluations should be done 9 and 18 weeks (+/- 3 days) after randomisation and thereafter every 18 weeks (+/- 1 week), according to local standard of follow-up, until PD or for maximum 15 months after randomisation. Beyond these 15 months or upon PD patients will enter the follow-up phase..

16.6.1. Recording of symptoms, adverse events and concomitant medications.

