2.2.3 Exploratory endpoints

 TTD is defined as the time from the randomization to treatment discontinuation for any reason (including progression of disease, treatment toxicity, refusal, lost to follow-up and death). Censoring for TTD (patients on treatment or completed treatment), will occur at the last-follow-up date

 DoR is defined as the time from the documentation of tumour response (either partial or complete response) to disease progression or death. Censoring will occur at the last tumour assessment with response other than progression.

2.2.4 (Serious) Adverse Events

Adverse Events (AEs)

The main criterion for treatment tolerability is the occurrence of toxicities and adverse events. The severity and causality will be classified according to the NCI CTCAE version 4 (http://evs.nci.nih.gov/ftp1/CTCAE/About.html).

An adverse event is defined as any untoward medical occurrence that occurs from the day of enrolment in the Remote Data Entry (RDE) until 100 days after the final dose of IMP regardless of whether it is considered related to a medication. The relation of the adverse event with the administered trial treatment has to be indicated as: unrelated, unlikely, possible, probable or definite. In addition, any known untoward event that occurs subsequent to the adverse event reporting period that the investigator assesses as possibly related to the protocol treatment should be considered an adverse event.

Immune-related Adverse Events (irAEs)

The following adverse events are of special interest and must be documented after randomization in both treatment arms:

CTCAE Version 4.0 system organ class / preferred terms:

Nervous system disorders:

- Peripheral motor neuropathy
- Peripheral sensory neuropathy
- Meningismus
- Limbic Encephalitis
- Nervous system disorders Other, specify (Guillain-Barré, myasthenia gravis, aseptic or non-infectious meningitis)

Skin and subcutaneous tissue disorders:

- Stevens-Johnson syndrome
- Toxic epidermal necrolysis
- Bullous dermatitis
- Rash acneiform
- Rash maculo-papular
- Pruritus
- Skin and subcutaneous tissue disorders Other, specify

Gastrointestinal disorders:

- Colitis

- Diarrhea
- Colonic perforation
- Small intestinal perforation
- Gastric perforation
- Gastrointestinal disorders Other, specify

Hepatobiliary disorders:

- Hepatic failure
- Hepatitis viral
- Drug-induced liver injury (DILI)

Investigations:

- Alanine aminotransferase increased
- Aspartate aminotransferase increased

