4.7 Safety analysis

The safety analysis will be based on the safety cohort, i.e., all patients who have received at least 1 dose of IMP treatment (experimental arm) plus all patients randomized to observation arm, and will include the following:

- Overview of the number of patients who experienced an AE and/or a SAE, as well as
 the number of patients in the safety cohort who did not experience an event, along with
 respective percentages will be shown. This information will be presented overall and by
 treatment arm. Also, number of patients that entered the study with baseline symptoms
 will be reported.
- Number of AEs/SAEs will be presented overall and by treatment arm.
- Number of patients experiencing a specific number of AEs/SAEs, overall and by treatment arm.
- Distribution of (S)AEs by grade and CTCAE category, separately for the two treatment arms. Six columns, one for each grade and one for all (any) grades, will be shown (for each arm). An additional column (by arm) indicating which events were also SAEs will be also available. In this column, the frequency of the SAEs and the severity grade will be given. The percentages that will accompany the frequencies will be based on the respective frequency of an event over the total number of patients in the safety cohort and specific treatment arm. This table will include all (S)AEs irrespective of their relation to the trial treatment.
- Analogous table focusing only on the treatment related (S)AEs.
- Number and corresponding percentages of treatment related (S)AEs by grade, leading either to treatment discontinuation or death will be summarized for the two treatment arms.

- Maximum severity of adverse events (AE/SAE) for patients, overall and by treatment arm.

- Number of SAEs by center
- Detailed information of pulmonary AEs/SAEs of grade ≥3 will be summarized for the two treatment arms.
- The risk difference between the two treatment arms, along with corresponding 95%
 CIs for specific adverse evets (most frequent i.e. ≥15%, of any grade, or perhaps focus on grade ≥3, irrespective of relation to treatment or treatment-related).

Analogous (more concise) information will be reported for the adverse events during the chemo-radiotherapy phase of all enrolled patients who received at least one dose of chemo-radiotherapy (per-protocol safety cohort).

5 Technical details

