- o In all other cases, the patient will be censored at the date of randomization plus 1 day.

Reporting conventions

Regarding the estimates presented in the report, the following rules will be adopted:

- P-values ≥0.001 will be reported with three decimal places
- P-values >0.010 will be reported with two significant demical digits
- P-values less than 0.001 will be reported as "<0.001"
- Means, medians, 95% confidence limits (Cis), quantiles, and any other summary statistics, will be reported with one decimal digit
- Hazard ratios (HRs) and their 95% CI's will be reported to two decimals
- Estimated parameters, not on the same scale as raw observations (e.g. regression coefficients) will be reported to three significant figures.

Multiple recordings of an event for the same patient

There are some cases where a patient may experience the same event (AE/SAE) more than once. In such cases, the event will be counted only once for the calculation of the total number of events reported for the overall safety cohort.

Presentation of results

The results will be presented through tables and figures. A summary of the results will also accompany the main report. First, a short synopsis of the results will be presented through bullets, where only the most important findings will be shown. Following that, a more detailed description of the results will be provided, sectioned in the following order:

- Patient accrual and baseline characteristics
- Follow-up and Treatment administration

- Efficacy analysis
- Safety analysis

All tables and figures will be included in an appendix.

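### The crude AE risk differences in SAP 4.7 need a common-window and a time-adjusted companion, because AE collection ends by a different rule, and is assessed at a different frequency, in each arm

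*SAP*

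**What the plan says.** **The contrast.** SAP 4.7 lists "The risk difference between the two treatment arms, along with corresponding 95"% confidence intervals, for AEs with a frequency of at least 15%. It leaves open whether the focus is any grade or grade ≥3, and whether events count "irrespective of relation to treatment or treatment-related". The estimator is not named. That it is crude follows from the rule for the tables in the same section: "The percentages that will accompany the frequencies will be based on the respective frequency of an event over the total number of patients" in the arm. SAP section 5 adds that for repeats in one patient "the event will be counted only once for the calculation of the total number of events reported for the overall safety cohort". No common cut-off, person-time rate, cumulative incidence or caveat on ascertainment is planned.

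**The collection window.** Footnote 14 of the protocol's trial schedule requires documentation of AEs "within 100 days of the last administered study medication or within 100 days after the last visit in the observation arm"; protocol 12.8 repeats this for SAEs. SAP 2.2.4, like protocol 12.1, instead runs the window "until 100 days after the final dose of IMP regardless" of relatedness. Observation patients receive no IMP, so that definition gives them no end date.

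**The assessment schedule.** Protocol 16.6 asks for evaluations before each dose in the experimental arm. In the observation arm "these evaluations should be done 9 and 18 weeks (+/- 3 days) after randomisation and thereafter every 18 weeks", until progression or 15 months. The AE form in protocol Table 16 follows the same pattern: after each IMP cycle in one arm, at weeks 9 and 18 and then every 18 weeks in the other. TSH, glucose, calcium, LDH, amylase and lipase are measured in the experimental arm only (16.6.9 and 16.6.10).

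**The concern.** A risk difference over all patients reads as a drug effect only if patients in both arms are watched for about the same time and with about the same intensity. Here neither is guaranteed.

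The experimental clock stops 100 days after the last dose. A progression-free patient who stops for toxicity therefore leaves AE collection early, while a progression-free observation patient stays in it until 15 months plus 100 days. The shortening depends on toxicity, which is the thing being measured. Denser visits and one-sided laboratory testing act on the recorded percentage in the other direction; hypothyroidism, for example, is an AE of special interest, but TSH is measured in one arm only.

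The stake is the comparative safety message of an open-label trial whose protocol (4.7) calls pulmonary toxicity an important question. The primary PFS analysis is not touched.

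**Working it through.** **1. The plan's own figure.** The protocol says that 15 months of observation correspond to completed consolidation. Four induction cycles of 21 days plus 12 months of maintenance give 84 + 365 = 449 days = 14.8 months, or 15.2 months with the permitted 14-day start lag. The figure reproduces.

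**2. Maximum windows from randomisation.**
- Experimental: from (449 − 14 + 100) days = 17.6 months, if the last dose falls 14 days before the end of the span with no start lag, to (449 + 14 + 100) days = 18.5 months.
- Observation: 15 months + 100 days = 18.3 months.

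These are essentially equal.

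**3. Realised windows.** Inputs are the design PFS medians of 13.1 and 22.8 months, and stops for related AEs of 11% (SCLC cohort, protocol 11.2.3) and 36.4% (melanoma trial, protocol 11.3). Assumptions: exponential PFS; toxicity stops spread uniformly over 3 or 15 months; last visit taken as progression or 15 months; a full 100-day tail (3.29 months) for everyone.

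For the observation arm, the mean is (1 − exp(−λ·15))/λ + 3.29 with λ = ln 2/13.1 = 0.0529. That is 10.35 + 3.29 = 13.6 months.

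For the experimental arm the window is min(PFS, toxicity stop, 15) + 3.29, simulated with 2,000,000 patients. To get the shift, one constant AE hazard is set in both arms so that the observation risk is 15% or 30%. The shift is the experimental minus the observation crude risk, so it comes from window length alone.

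| Experimental-arm assumption | Mean window (months) | Ratio to observation | Shift, 15% AE (points) | Shift, 30% AE (points) |
|---|---|---|---|---|
| PFS 22.8, no toxicity stops | 15.3 | 1.12 | +1.8 | +3.3 |
| PFS 22.8, 11% stop within 3 months | 14.2 | 1.04 | +0.5 | +0.9 |
| PFS 22.8, 36.4% stop over 15 months | 13.3 | 0.98 | −0.3 | −0.6 |
| PFS 22.8, 36.4% stop within 3 months | 11.5 | 0.84 | −2.3 | −4.5 |
| PFS 13.1 (no benefit), 36.4% stop within 3 months | 10.4 | 0.76 | −3.4 | −6.6 |

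The documents do not define the last visit. If it is the end-of-treatment visit, up to 30 days later, the observation mean rises to 14.6 months and the range of ratios becomes 10.4/14.6 = 0.71 to 15.3/14.6 = 1.05.

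**4. Assessment intensity.** Experimental: 4 induction cycles plus 365/14 ≈ 26 maintenance doses = 30. Observation: weeks 9, 18, 36 and 54 = 4, since 15 months is week 65 and the next visit would be week 72. The end-of-treatment visit (protocol 16.8), which also records AEs, makes it 5. The ratio is 30/4 = 7.5, or 31/5 = 6.2 with that visit counted in both arms.

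**5. What a 100-day window covers.** Every experimental patient in the safety cohort has at least one dose, given after randomisation, so collection runs to at least day 100. Observation patients are covered by their own 100-day tail. Inside it, the observation arm has one scheduled assessment (week 9 = day 63; week 18 = day 126). The experimental arm has four induction doses and, with maintenance starting on day 84 to 98, one or two maintenance doses: about 5 or 6 to 1.

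**The case against.** **The windows were matched on purpose.** Both arms have a 100-day tail, and the observation phase is sized to completed treatment. This stands. A reader might infer from the two stopping rules that the windows differ greatly and that observation time dominates the contrast. For example, a stop at dose 2 gives 5 weeks + 100 days = 4.4 months, against 18.3 months for a progression-free observation patient. At a constant rate, a 20% risk over 4.4 months becomes 1 − exp(ln 0.8 × 18.3/4.4) = 60% over 18.3. The documents do not support that reading: it sets two opposite extremes side by side. Observation patients who progress early also leave early, and experimental patients who complete treatment have about 18 months.

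**Late drug-related events are still reportable.** Protocol 12.1 and SAP 2.2.4 count later events judged possibly related as AEs, and protocol 12.5.2 requires late related fatal, life-threatening and other medically significant events. This stands for related events and softens any loss in patients who stop early. It does not help an all-cause contrast, and relatedness is judged unblinded.

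**The safety analysis is descriptive.** Protocol 18.4 speaks of tabulation, no AE test is planned, CT follows one schedule in both arms, and SAP 4.7 already tabulates SAEs and grade ≥3 pulmonary events. This stands and limits the weight of the point. A crude difference remains a valid description of recorded AEs. The gap is that nothing guards against reading it as a treatment effect.

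**A 100-day contrast has its own faults.** It omits nearly all of maintenance. It can also cut into the period of radiation pneumonitis, which protocol 4.7 puts mostly at 2 to 6 months after radiation. Nor does it cure the visit imbalance. This stands, and it is why that contrast should not replace the full-window tables.

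**Conclusion.** The point holds in a limited form. By design the maximum windows agree; realised windows may not, because only the experimental clock is cut short by a toxicity stop. The effect of window length alone is moderate: −6.6 to +3.3 points for a 30% AE and −3.4 to +1.8 points for a 15% AE. Toxicity stops pull it down and longer PFS pushes it up, so the documents do not settle its direction. These figures rest on constant hazards, exponential PFS at the design medians, uniform stop times, and discontinuation rates from other trials; they are a range, not a forecast.

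The unequal ascertainment is a separate issue and more certain in direction: it tends to raise low-grade and laboratory AEs in the experimental arm. Its size cannot be computed from the documents. Neither effect is reflected in the planned confidence interval. The missing observation-arm end date in SAP 2.2.4 is a wording gap, since footnote 14 governs collection.

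**What to change.** Amend the SAP as follows; the data are already collected.

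1. In 4.7, keep the crude risk difference and add beside it (a) the risk difference for the first 100 days after randomisation, for safety-cohort patients alive and in follow-up, and (b) as support, the cumulative incidence of first AE or exposure-adjusted rates over the full window.
2. Make the contrast for grade ≥3 events and SAEs a firm rule instead of an option, since these depend less on visit frequency.
3. State that visit and laboratory schedules differ between arms, and that any-grade and laboratory differences are to be read with that in mind.
4. In 2.2.4, give the observation-arm window in line with footnote 14, and say which visit counts as the last.

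The cost is some wording and a few table columns. The 100-day contrast leaves out most of maintenance and late pneumonitis, so it supplements the full-window tables. Neither addition removes the visit-frequency bias; item 3 only makes it visible.

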## **12. Adverse events and reporting**

### **12.1. Adverse event reporting**

The main criterion for tolerability is the occurrence of toxicities and adverse events. The severity and causality will be classified according to the NCI CTCAE Version 4. The CTCAE is available for downloading on the internet, see appendix 3 (<http://evs.nci.nih.gov/ftp1/CTCAE/About.html>).

An adverse event is defined as any untoward medical occurrence that occurs from the day of enrolment in the RDE until 100 days after the final dose of IMP, regardless of whether it is considered related to the trial treatment. The relationship of the adverse event with the administered trial treatment has to be indicated (unrelated – unlikely – possible – probable – definite).

In addition, any known untoward event that occurs subsequent to the adverse event reporting period that the investigator assesses as possibly related to the protocol treatment should be considered an adverse event.

Symptoms of the targeted cancer (if applicable) should not be reported as adverse events.

The adverse event severity grade provides a qualitative assessment of the extent or intensity of an adverse event, as determined by the investigator or as reported by the patients. The severity grade does not reflect the clinical seriousness of the event, only the degree or extent of the affliction or occurrence (e.g. severe nausea, mild seizure), and does not reflect the relationship to study drug.

Severity grade for other adverse events not covered in the toxicity grading scale:

1 = Grade 1	Mild
2 = Grade 2	Moderate
3 = Grade 3	Severe
4 = Grade 4	Life-threatening
5 = Grade 5	Fatal

Note:

- Baseline symptoms will be recorded on the eCRF and changes in grade as well as resolution of an AE during treatment have to be reported
- Laboratory abnormalities for non-safety parameters will be documented on the AE eCRF from Grade  $\geq 3$  only
- AEs should not be reported in a narrative description.

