1.3 Trial treatment

After enrolment, the patient will receive or, if included after the first chemotherapy cycle, continue receiving standard of care treatment for limited disease SCLC consisting of chemoradiotherapy and PCI.

- Chemotherapy: will be started in the week following enrolment (alternatively, maximum 1 cycle of chemotherapy may be administered before enrolment), and consists of a total of 4 cycles of cisplatin (25 mg/m2 i.v. on days 1 3 or 75 mg/ m2 on day 1) or carboplatin (AUC 5-6, calculated according Calvert formula, i.v. on day 1), plus etoposide (100 mg/ m2 i.v. days 1 3), repeated every 3 weeks (+/- 3 days without cycle delay).
- Concomitant Thoracic Radiotherapy: Accelerated twice-daily administration of 45 Gy in 30 twice-daily fractions of 1.5 Gy (6-8 hours apart), 5 days per week for 3 weeks, or an allowed, but not-recommended schedule of 56 Gy, given in 28 once-daily fractions of 2 Gy, 5 days per week for 6 weeks. Two options are allowed: Thoracic radiotherapy MUST start either from day 1 of cycle 1 or day 1 of cycle 2. Radiotherapy start at day 1 of cycle 3 is allowed if patient is enrolled after the first cycle only but should be exceptional. Optimally, radiotherapy should start at the latest on day 1 of cycle 2.
- PCI: 25 Gy in 10 fractions starting between day 8 and day 15 of chemotherapy cycle 4 and finished not later than day 29 from start of cycle 4.

After_randomization, which should take place within 5-6 weeks after day 1 of cycle 4 (between days 35 and 42 of cycle 4)

Experimental arm

Induction phase:

To start within 6-8 weeks (42-56 days) after the start of chemotherapy cycle 4, and not more than 2 weeks (14 days) after the date of randomization.

- Nivolumab at a dose of 1 mg/kg i.v. over a period of 30 minutes,
 followed (on the same day) by
- Ipilimumab at a dose of 3 mg/kg i.v. over a period of 90 minutes, once every 3 weeks (+/3 days, without dosing delay), 4 cycles

Maintenance phase:

To start 3 weeks (21 days) after the last Investigational Medical Product (IMP) dose of induction phase.

Nivolumab 240 mg i.v. over a period of 30 minutes, once every 2 weeks (+/- 2 days, without dosing delay), for a maximum of 12 months from start of maintenance phase.

Observation arm

No further treatment.

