2.3 Analysis population

Efficacy cohort: The efficacy cohort is the Intention-to-treat (ITT) population of the trial and includes all randomized subjects under protocol AM1. Patients will be evaluated in the treatment arms to which they were randomly assigned, regardless of the treatment actually received, including patients who were randomized but did not receive any trial treatment.

Safety cohort: The safety cohort consists of all subjects who have received at least one dose of IMP treatment plus all patients randomized to observation arm (under protocol AM1).

Patients will be evaluated according to the treatment they actually received, irrespective of their allocated treatment at randomization.

Per-Protocol cohort: Per-protocol cohort includes all patients enrolled under protocol AM1.

Per-Protocol safety cohort: Per-protocol safety cohort includes all patients enrolled under protocol AM1, who received at least one dose of chemo-radiotherapy after enrollment.

3 Primary efficacy analysis of PFS

Primary efficacy analysis of PFS (primary endpoint) will be performed on **all randomized patients under AM1 protocol, based on their initial treatment assignment (ITT, efficacy cohort)**. PFS time is measured from time of randomization.

Formal hypothesis testing

Based on the protocol AM1 and after the modifications arose from the premature study accrual termination, the trial is designed to test the hypotheses that treatment with chemoradiotherapy and PCI followed by consolidation treatment (nivolumab plus ipilimumab) will lead to an increase in median PFS to 22.8 months, from 13.1 months under treatment with chemoradiotherapy and PCI without consolidation treatment. According to the study design, this corresponds to a PFS HR of 0.57. Using 80% power and a one-sided type I error of 5%, a total of 81 PFS events are needed to observed in order to achieve the trial goal.

In the frame of final efficacy analysis, the **formal comparison** of the PFS between the two treatment arms, will be based on **stratified log-rank test** (with number of fractions of radiotherapy [1/2] and administration of FDG-PET-CT [Yes/No] being the stratification factors). Unstratified log-rank test will be also calculated. This would be of particular value in case at least one stratum level has very low number of patients.

Further PFS analyses

The following **PFS analyses** will also be performed and presented

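### SAP 4.7 lets the between-arm adverse-event risk difference be computed on treatment-related events, a contrast that mixes event risk with unblinded attribution

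*SAP*

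**What the plan says.** SAP 4.7 describes safety mainly by tabulation. It plans a by-arm table of all adverse events whatever their cause, then an "Analogous table focusing only on the treatment related (S)AEs". It also plans a summary of related events "leading either to treatment discontinuation or death will be summarized for the two treatment arms". The final bullet goes beyond tabulation: "The risk difference between the two treatment arms, along with corresponding 95" per cent confidence intervals, for the most frequent events or perhaps those of grade 3 and above, "irrespective of relation to treatment or treatment-related". It does not say whether one or both of these event sets will be used, or which takes precedence.

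The safety cohort is "all subjects who have received at least one dose of IMP treatment plus all patients randomized to observation arm" (SAP 2.3). For the observation arm, SAP 1.3 states: "No further treatment".

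On attribution, Protocol 12.1 says "The relationship of the adverse event with the administered trial treatment has to be indicated", and SAP 2.2.4 repeats it with a five-level scale: "The relation of the adverse event with the administered trial treatment has to be indicated as: unrelated, unlikely, possible, probable or definite". Neither names a component of treatment. SAP 1.3 lists chemotherapy, thoracic radiotherapy, PCI and the two antibodies together under trial treatment. Protocol 12.5.1 instead defines a related event by a reasonable possibility of a link to the investigational drug. Protocol section 11 limits the investigational products to nivolumab and ipilimumab.

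**The concern.** A risk difference with a confidence interval reads as an estimate of what the drug adds. For all-cause events that reading is broadly fair, because the control arm supplies the background rate. For related events it is not. The observation arm has no treatment after randomisation to which an event could be attributed, except earlier chemo-radiotherapy and PCI. Investigators know the allocation when they judge causality. The same clinical event can therefore be counted in one arm and not in the other.

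Attribution is hardest for pneumonitis. Protocol 4.7 puts radiation pneumonitis at 15–20%, mostly two to six months after radiation, so many cases would arise after randomisation in both arms. The protocol wants to know whether the antibodies make it worse. The primary PFS analysis is not touched. What is at stake is the toxicity contrast that readers would weigh against any PFS benefit.

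**Working it through.** The documents give no hypothesis, power or alpha for adverse-event risk differences, so there is no plan figure to reproduce. The check is a reading of the definitions followed by an illustration.

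**Step 1. The two definitions.**
- *Related means related to the investigational drug (Protocol 12.5.1).* The observation arm is zero by construction. The risk difference is the attributed rate in the experimental arm, presented as a comparison.
- *Related means related to the administered trial treatment (Protocol 12.1, SAP 2.2.4), taken to include chemo-radiotherapy.* Investigators judge chemo-radiotherapy alone in one arm and chemo-radiotherapy plus antibodies in the other.

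**Step 2. What is estimated.** Let p be the true event risk and a the probability that an event is called related, with E for experimental and O for observation.

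- All-cause difference: p_E − p_O
- Related difference: p_E·a_E − p_O·a_O
- With equal true risk p, the related difference is p(a_E − a_O). This is zero only if attribution is equal.
- In the investigational-drug case (a_O = 0), the related difference equals the true excess only if p_E·a_E = p_E − p_O. With p_O = 0.20 and p_E = 0.30, that requires a_E = 0.10/0.30 = 1/3. Nothing in the conduct of the trial ensures it.

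**Step 3. Illustration with a true difference of zero.** Inputs:
- p = 15% or 20%, the background radiation pneumonitis range in Protocol 11.4 and 18.5.
- n = 130 per arm, from 260 planned at 1:1 (SAP 1.4.1).
- a_E and a_O are assumptions; no document gives them.

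With r = p·a, SE = √[r_E(1−r_E)/n + r_O(1−r_O)/n], and the interval is the difference ± 1.96 SE. For p = 0.20, a_E = 0.8, a_O = 0: r_E = 0.16, SE = √(0.16×0.84/130) = 0.032, giving 16.0 points (9.7 to 22.3).

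| p | a_E | a_O | Related difference, points (95% CI) | All-cause expectation |
|---|---|---|---|---|
| 15% | 0.8 | 0 | 12.0 (6.4 to 17.6) | 0 |
| 15% | 0.8 | 0.25 | 8.25 (1.8 to 14.7) | 0 |
| 15% | 0.8 | 0.5 | 4.5 (−2.7 to 11.7) | 0 |
| 15% | 0.8 | 0.8 | 0 (−7.9 to 7.9) | 0 |
| 20% | 0.8 | 0 | 16.0 (9.7 to 22.3) | 0 |
| 20% | 0.8 | 0.25 | 11.0 (3.7 to 18.3) | 0 |
| 20% | 0.8 | 0.5 | 6.0 (−2.1 to 14.1) | 0 |
| 20% | 0.8 | 0.8 | 0 (−8.9 to 8.9) | 0 |

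With a_O = 0 and a_E from 0.5 to 1.0, the spurious difference runs from 0.15×0.5 = 7.5 to 0.20×1.0 = 20 points.

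**Step 4. Fewer patients.** Accrual closed early (SAP 1.4.2) and the documents do not give the number randomised. Take 75 per arm as an assumption and a true risk of 15% in both arms. If all experimental events are called related, against 2 percentage points of observation patients, the difference is 13 points: SE = √(0.15×0.85/75 + 0.02×0.98/75) = 0.044, CI 4.3 to 21.7. If half the observation events are called related, it is 7.5 points (CI −2.5 to 17.5).

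**Step 5. When there is a real excess.** With p_O = 0.15 and p_E = 0.25, the all-cause difference is 10 points. The related difference is 0.25×0.8 = 20 points if a_O = 0, and 0.25×0.8 − 0.15×0.5 = 12.5 points if a_O = 0.5.

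**The case against.** The strongest reply is that the plan already holds what is needed. SAP 4.7 has a full all-cause table by arm and grade, maximum severity by arm, and a summary of pulmonary events of grade 3 and above with no relatedness filter. Protocol 12.3 requires pneumonitis to be documented after randomisation in both arms. The early safety evaluation in Protocol 18.5 states no relatedness criterion. The disputed bullet itself allows the all-cause version. Protocol 18.4 says safety is described by tabulation, and no test or decision rule rests on the risk difference. All of this stands. It means that the related-event difference is not a designated headline result and that the pneumonitis question does not hang on attribution alone. It does not make the related-event difference interpretable if it is computed.

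A reader might also infer that the case report form holds one relatedness field pooling chemo-radiotherapy with the antibodies. The documents do not show that. The form is not included. Protocol 12.5.1 ties relatedness to the investigational drug. Protocol 10.7.4.5 asks for the relationship to ipilimumab and nivolumab when ipilimumab alone is stopped. Protocol Table 16 has separate adverse-event forms for the chemo-radiotherapy phase and for the period after randomisation, although ongoing events are entered again on the second. What can be said is that the target of attribution is defined inconsistently.

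Nor are the by-arm tables of related events wrong in themselves. They are descriptive, and the observation column shows how often late toxicity is attributed to earlier treatment. The discontinuation part of the related-event summary has no meaning for an arm with no treatment to stop, but that is a matter of labelling.

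**Conclusion.** The point holds for the risk difference. Under either definition of related, the contrast mixes event risk with unblinded attribution and does not estimate a drug effect. With equal true risk it can show an excess whose interval excludes zero: 12 to 16 points at a true risk of 15–20%, 130 per arm, a_E = 0.8 and a_O = 0. The attribution probabilities are assumptions. When half the observation-arm events are also called related, the excess falls to 4.5–6 points with intervals covering zero. The figures show that the bias can be material; they do not predict its size in this trial.

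The all-cause difference is not perfect either. Its zero expectation assumes equal detection, and observation patients are seen less often (Protocol 16.6). It also uses the safety cohort rather than everyone randomised. It does remove the dependence on attribution.

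The consequence is confined to how toxicity is presented. The PFS conclusion is unaffected.

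**What to change.** In the last bullet of SAP 4.7, delete the final two words of "irrespective of relation to treatment or treatment-related" and state that between-arm risk differences use all-cause adverse events after randomisation only.

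Keep the tables of related events, and of related events leading to discontinuation or death, as description without a between-arm risk difference or interval. State for each whether related means related to the investigational products or to chemo-radiotherapy, and reconcile Protocol 12.1 and SAP 2.2.4 with Protocol 12.5.1 on this.

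Do not move events that occur after randomisation into the chemo-radiotherapy table at the end of SAP 4.7. That table is defined by phase and by a different cohort (all enrolled patients who received chemo-radiotherapy), and late radiation events belong in the comparison after randomisation.

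The cost is a few lines of SAP wording, with no new data and no change to the design.
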